The role of the bacterial flora in the pathogenesis of pouchitis has been strongly suggested by clinical trials demonstrating a high clinical efficacy of antibiotics (e.g. ciprofloxacin, metronidazole) to treat and prevent pouchitis. There seem to be a bacterial dysbiosis present in patients with pouchitis ¹³⁻¹⁶. Studies comparing the bacterial flora of pouches of patients with FAP and UC found sulfate reducing bacteria in the majority of UC patients but none in FAP patients ¹⁷. Also strict anaerobes (Clostridium perfringens, Bifidobacteria and Bacteroides) predominate over facultative anaerobes (Enterococci, Coliforms and Lactobacilli) in stool and mucosal biopsies of UC patients ¹⁸. Using a 16S ribosomal RNA technique to determine qualititativ changes in the mucosa of the pouch, Komaduri et al. report the persistence of Fusobacter and Enteric species and the absence of specific bacteria such as Streptococcus species in association with pouchitis ¹⁶. More recently an increase in Ruminococcus gnavus, Bacteriodes vulgatus and Clostridium perfringens with a concomitant reduction of Lachnospiraceae Blauatia and Roseburia before colectomy was found to be a risk factor for developing pouchitis in the first year after IPAA.¹⁹

• Current therapeutic approaches for pouchitis

Different antibiotic therapies including ciprofloxacin, metronidazole, rifaximin have been shown to successfully treat pouchitis in subgroups of patients ²⁰⁻²⁴. The probiotic VSL#3, which is a highly concentrated bacterial cocktail of 8 different bacterial species, prevents acute and chronic pouchitis, but is only effective in a subgroup of patients ²⁵⁻²⁹. Agents known to be efficacious in left-sided ulcerative colitis including budesonide enemas ³⁰, mesalamine enemas ³¹ and suppositories ³², butyrate and glutamine suppositories ³³ have all been used with some success. Allopurinol, inulin and bismuth carboner foam enemas were also investigated without significant clinical efficacy ³⁴⁻³⁶. More recently a single center study described a therapeutic efficacy of AST-120, a spherical carbon adsorbent in acute pouchitis ³⁷. A placebo-controlled trial has to confirm these findings in the future.

3. RATIONALE FOR THIS STUDY

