5. TRIAL ENDPOINTS

• Primary Endpoint:

Safety and Tolerability of FMT

• Number of study patients, who discontinued therapy

- Adverse events grouped by body system
- Changes in laboratory values
- Secondary Endpoints
- Clinical remission (mPDAI score ≤ 4 points) and no need for antibiotic therapy at week 4.
- Clinical remission (clinical mPDAI score ≤ 4) and no need for antibiotics at week 8*.
- Clinical remission (clinical mPDAI score ≤ 4) and no need for antibiotics at week 16*.
- Endoscopic improvement of active pouchitis (decrease from baseline in mPDAI endoscopic subscore ≥ 2 points) at week 4.
- Response: Symptomatic improvement of active pouchitis (decrease from baseline in mPDAI clinical subscore ≥ 2 points) and no need for antibiotic therapy at week 4.
- Response: Symptomatic improvement of active pouchitis (decrease from baseline in mPDAI clinical subscore ≥ 2 points) and no need for antibiotic therapy at week 8*.
- Response: Symptomatic improvement of active pouchitis (decrease from baseline in mPDAI clinical subscore ≥ 2 points) and no need for antibiotic therapy at week 16*.

*Only patients who do not continue in open label extension

- Exploratory analyses (OL=Open label):
- Endoscopic improvement of active pouchitis (decrease from baseline in mPDAI endoscopic subscore ≥ 2 points) at in open label extension week 8.
- Clinical remission (mPDAI score ≤4 points and a decrease in the baseline mPDAI> 2 points) and no need for antibiotic therapy at week 10 OL.
- Clinical remission (clinical mPDAI score ≤ 4) and no need for antibiotics at week 14 OL.
- Clinical remission (clinical mPDAI score \leq 4) and no need for antibiotics at week 22 OL.
- Response: Symptomatic improvement of active pouchitis (decrease from baseline in mPDAI clinical subscore ≥ 2 points) and no need for antibiotic therapy at week 10 OL.
- Response: Symptomatic improvement of active pouchitis (decrease from baseline in mPDAI clinical subscore ≥ 2 points) and no need for antibiotic therapy at week 14 OL.
- Response: Symptomatic improvement of active pouchitis (decrease from baseline in mPDAI clinical subscore ≥ 2 points) and no need for antibiotic therapy at week 22 OL.
- Symptomatic worsening of active pouchitis (decrease from baseline in mPDAI clinical subscore ≥ 2 points) from FMT week 0 week 16
- Quantitative changes in mPDAI from baseline values
- Quantitative changes of calprotectin from baseline
- Alterations in stool microbiome after FMT

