- Well-founded doubt about the patient's cooperation
 - Concomitant Medications

All antibiotic therapies have to be stopped 1 day before FMT.

Following drug groups are permitted as concomitant medication:

- Orally administered mesalazine containing drugs should be stable for the last 4 weeks
- Local therapies containing 5-ASA (enemas, suppositories) or steroid enemas should be at a stable dose 2 weeks before inclusion in the study.

Following drug groups are **not** permitted as concomitant medication:

- Antibiotic therapy for treatment of pouchitis
- Cytostatics/immunosuppressants, cyclosporine, tacrolimus, mycophenolate mofetil.
- Anti-TNF therapies or anti-adhesion therapy.
- Non steroidal anti-inflammatories (NSAIDs) as long-term treatment, defined as use for at least 4 days a week each month

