At phone visit 4 the coordinator will ask the study patient if adverse events occurred and review the adverse event diary. The coordinator will evaluate the clinical components of the mPDAI of the last 3 days before the phone call (stool frequency, rectal bleeding, fecal urgency/ abdominal cramping, fever) as well as the concomitant medications. If the patient is in remission according to the diary (mPDAI \leq 4) and is on no concomitant medications, a pouchoscopy will be planned for site visit 5. If the study patient is not in remission (mPDAI \geq 4) or had an early relapse after FMT the open label extension will be offered and the patient can be started on oral antibiotics again. For safety analyses a site visit 5 should be planned in the following 3-4 days. If the study patient chooses not to participate, he should be followed according the same schedule as patients who are in remission.

Early termination visit due to flare on day 1-28 after FMT or due to adverse event or patient unwillingness to continue in study necessitating early termination

If at any time between day 1-28 after endoscopic FMT the patient experiences recurrence of his pouchitis symptoms, he/she will contact the coordinator. The coordinator will ask the study patient if adverse events occurred and review the adverse event diary. The coordinator will evaluate the clinical components of the mPDAI of the last 3 days before the phone call (stool frequency, rectal bleeding, fecal urgency/ abdominal cramping, fever) as well as the concomitant medications.

If the study patient has active disease (mPDAI>4), an early termination study visit will be scheduled. A physical exam will be completed and, if possible, stool will be collected before the start of antibiotic therapy as standard of care. Blood labs will also be collected. The patient will be started on the same antibiotic, which he was on before entering the study. At the study visit the coordinator will review possible adverse events, evaluate the clinical components of the mPDAI of the last 3 days before the visit (stool frequency, rectal bleeding, fecal urgency/ abdominal cramping, fever) as well as the concomitant medications. If the patient wants to proceed into the open label study, he has to undergo at least 10 days of standard of care antibiotic therapy, before he can undergo the open label therapy with FMT (endoscopic and oral FMT).

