Dispense oral FMT or placebo Dispense omeprazole 20 mg (1 tablet) daily for 14 days during oral FMT Dispense PDAI diary Dispense adverse events diary

Pouchoscopy: Evaluation of endoscopic PDAI and perform "blinded" (real or placebo) FMT.

• Visit 2: Phone visit week 1 (7 (+1 day) days after endoscopic FMT /placebo and on oral FMT/placebo)

Formal aspects:

Adverse events (review adverse events diary)

Concomitant medication

Calculation of clinical mPDAI (stool frequency, rectal bleeding, fecal urgency/abdominal cramping, fever)

• Visit 3: Site visit week 2 (15 +3 days after endoscopic FMT /placebo and on oral FMT/placebo)

Formal aspects:

Adverse events (review adverse events diary)

Concomitant medication

Calculation of clinical mPDAI (stool frequency, rectal bleeding, fecal urgency/abdominal cramping, fever)

Reminder stool collection on day 15, 16 or 17 (day 1-3 after end of oral FMT) and bring in stool.

• Visit 4: Phone visit week 4 (2-3 days before planned week 4 site visit)

Formal aspects:

Adverse events (review adverse events diary)

Concomitant medication

Reminder to bring stool day 25, 26 or 27.

Calculation of clinical mPDAI (stool frequency, rectal bleeding, fecal urgency/abdominal cramping, fever)

If patient is in clinical remission (mPDAI ≤ 4) and no need for antibiotics plan for pouchoscopy week 4

If patient is not in clinical remission (mPDAI > 4) or need for antibiotics or comes in due to exacerbation of symptoms with possibility to continue with open label extension. Need to restart 10 day course of antibiotics as standard of care similar to initial antibiotic treatment before the first FMT

• Visit 5: Site visit Week 4 (day 28 +/- 3 days after first transplant) or early termination visit due to flare (day 1-28 after first transplant)

Examinations

Vital signs: blood pressure (mm Hg), heart rate (min-1), weight (kg), temperature

Physical examination:

- Head (including ENT and eyes)
 Lymphatic system
 Endocrine system
 Lungs and respiratory tract
 Peripheral vascular system
 Skin and connective tissue
- Cardiovascular system

- Other

each: actual status: Present finding / normal condition / not examined

Measurement of laboratory parameters

Hematology Serum chemistry

Stool collection: Bring to visit.

Formal aspects:

Return of study medication (empty containers)

Compliance assessment (count of empty containers returned)

Concomitant medication

Adverse events (review adverse events diary)

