The primary endpoint is the evaluation of safety and tolerability of FMT in patients with ADP. Secondary endpoints are endoscopic and clinical remission at week 4 in conjunction with no need for antibiotic therapy, clinical response and remission and no need for antibiotics at week 4,8 and 16, endoscopic improvement of pouchitis and quantitative changes of calprotectin after the initial FMT. All subjects with missing data for determination of endpoint status will be considered as a non-responder in the intention-to-treat analysis. For dichotomous outcomes we will compute the percentage of subjects having the event along with a 95% confidence interval. For continuous outcomes we will compute the mean and a 95% confidence interval for the mean as well as descriptive statistics such as median, range and upper and lower quartiles. In addition to computing these measures for all 20 subjects, we will compute them for subgroups of interest (e.g. endoscopic active vs inactive ADP). These estimates can then be used in the planning of a larger, hypothesis-based study.

• Sample size calculation

This trial is designed as a proof-of-concept study of FMT therapy, not a definitive evaluation of FMT therapy in patients with ADP. The goal is to evaluate the safety and feasibility of such a trial, as well as to estimate the effect sizes in placebo and FMT therapy groups in order to accurately estimate the sample size needed for subsequent evaluation in a larger definitive trial. Nonetheless, we estimated the minimum effect size this pilot study can detect. We assume a placebo remission rate (defined as clinical remission and no need for antibiotics) of 10%. The low placebo response rate is based on the inclusion criterion, which selects only patients needing continuous or recurrent antibiotic therapy in the setting of ADP. With a follow-up of 16 weeks with the requirement of clinical remission without antibiotic therapy at end of follow-up, a placebo response rate beyond 10% is highly unlikely. The recent case series of Stallmach et al. suggests an antibiotic-free remission rate of 80% and a response rate of 100% in the setting of repeated FMT.⁴⁹ With 20 patients (1:1 randomization), and a placebo response rate of 10%, we will have 80% power to detect an effect difference of 67.5%, that is, an antibiotic-free remission rate

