of 77.5% in the treatment group (2-sided, alpha=0.05, Fisher-Irwin's exact conditional test). Thus, even with this small proof-of-concept design, we could observe a significant effect in the range of effect size reported in recent case series.

Microbiome Analyses

From each patient 1 stool sample will be collected before transplant and twice after the transplant (week 3 and 4). Patients in remission will collect 2 more stool samples in week 8 and 16. Patients in the open label extension trial will collect stool samples after transplant in week 8, 10, 14 and 22. Assuming that 9 patients enter remission in the placebo controlled phase (9x4= 36 samples) and 11 patients enter the open label extension (11x7=77 samples) a total of 116 samples will be analysed. All microbiome analyses will be conducted by OpenBiome, which will donate time and materials for the analyses. The gut microbiome of donors and patients will be analysed through deep sequencing of the 16S ribosomal RNA gene amplified from stool samples. Microbial engraftment will be operationalized through the donor similarity index (DSI) used to evaluate the degree of engraftment in FMT recipients over time (after 2,4,8 and16 weeks).⁶¹ We will measure DSI over time to elucidate the stability of engraftment and its relationship to clinical observations. In addition to 16S rRNA sequencing, we will save aliquots of stool for metabolomic characterization. In particular, given the potential role of butyrate in ameliorating inflammation, we're especially interested in measuring short chain fatty acid levels in stool before and after FMT. We plan to collect stool samples for characterization at baseline and at 2, 4, 8 and 16 week intervals after treatment.

21. STUDY VISITS CHART

1.1 STUDY VISITS CHART PLACEBO CONTROLLED TRIAL SCREENING – WEEK 4 (SITE VISIT)

Visit	Screening	1	2	3	4	5	Early termination ^g
Type of visit	Site	Site	Phone	Site	Phone	Site	Phone/site
Derr	-14	0	7	15	26	28	
Day	-14	0	+/-1	+3	+/-1	+/-3	
Week	-2	0	1	2	4	4	
Medical History	Х						
mPDAI score		Х	Xd	X ^d	X ^{g(!)}	Х	X
Concomitant Medication	Х	Х	X	X	X	Х	X
Adverse Events		Х	X	Х	Х	Х	X
Physical Exam	Х					Х	Х
Blood Tests	Х					Х	Х
Pregnancy Test (urine)	Х	Х					
Test FMT capsule	Х						
Dispense FMT capsules		Х					
10-14 day antibiotic therapy pre- transplant	Х				Xc	Xc	Xc
Stool sample	Xe			X ^f	X ^f	X ^g	Х
Sigmoidoscopy (Pouchoscopy		Х				Xa	
Endoscopic FMT		Х					
Distribute/Review Subject Diaries ^b	Х	Х	Х	Х	Х	Х	Х

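### Remission and response are disqualified only by antibiotics, so escalated 5-ASA or steroid use has no scoring rule, and the sections disagree on who gets the week-4 pouchoscopy

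*Combined protocol and SAP*

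**What the plan says.** **Endpoints.** Sections 1, 5 and 20 list clinical remission and symptomatic response at weeks 4, 8 and 16. The score thresholds vary somewhat between sections, but the drug condition does not. At week 4 in Section 5, for example, both definitions end "and no need for antibiotic therapy at week 4". The sample size rationale in Section 20 uses the same antibiotic-free remission.

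**Permitted medicines.** Section 6 (Concomitant Medications) allows oral mesalazine that has been stable for 4 weeks, and says that topical 5-ASA or "steroid enemas should be at a stable dose 2 weeks before inclusion in the study". No section requires these to stay unchanged after week 0. Steroids are an entry exclusion in Section 6 but are absent from its list of medicines not permitted on study. That list does bar immunosuppressants, anti-TNF and anti-adhesion therapy. Section 2 says of several topical agents for pouchitis, budesonide and mesalamine enemas among them, that they "have all been used with some success".

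**Withdrawal.** Section 8 (Visit 5) gives a need for, or increase of, steroids as a lack-of-efficacy reason for premature withdrawal. Section 16 gives disease progression needing another treatment as an example of a reason to withdraw a patient, and asks for a final mPDAI in everyone who stops early. Section 20 (Clinical analyses) counts missing endpoint data as non-response.

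**Week-4 pouchoscopy.** Under Section 7, if the patient is in remission by diary and "is on no concomitant medications, a pouchoscopy will be planned for site visit 5". Under Section 8 (Visit 4) the patient must be in clinical remission "and no need for antibiotics plan for pouchoscopy week 4", and Visit 5 repeats the antibiotic condition. Footnote a to the visit charts in Section 21 sets a score condition and no drug condition.

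**The concern.** The trial is meant to give remission and response rates per arm for planning a larger study. Two features of the text could put patients in the wrong category.

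First, a patient may drift back into symptoms after week 0 and be controlled by starting or increasing 5-ASA or a steroid preparation. If the score criterion is met without antibiotics, nothing in the endpoint text stops that patient counting as a success. If this happens more in the arm with more relapse, which is expected to be placebo, the difference between arms shrinks.

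Second, the Section 7 condition covers all medicines, including those that Section 6 permits. A remitter on stable mesalazine satisfies Section 8 but not Section 7. Without a pouchoscopy there is no endoscopic subscore, so a true remitter could be lost to the missing-data rule.

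**Working it through.** **Step 1. The plan's own power figure.** Inputs from Section 20: "With 20 patients (1:1 randomization), and a placebo response rate of 10"%; "we will have 80% power to detect an effect difference of 67.5"%; a remission rate "of 77.5% in the treatment group (2-sided, alpha=0.05, Fisher-Irwin's exact conditional test"). With 10 per arm, exact power is the sum over all outcomes (a, b) of Bin(a; 10, 0.10) × Bin(b; 10, 0.775), taken where the two-sided Fisher p-value is at most 0.05. This gives 0.8016, or 80.16%, against the stated 80%. The figure reproduces; there is no arithmetic error. A normal approximation would give 93.0%, so the exact test was indeed the one used.

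**Step 2. Can an escalated patient be scored as a success?**
- Endpoint text: only antibiotics disqualify.
- Section 6: stability is required before inclusion only.
- Section 8, Visit 5: covers steroids, not 5-ASA, and sets a withdrawal reason, not an endpoint status.
- Section 16: withdrawal for another treatment is an example, and a final mPDAI is still wanted.
- Section 20: only missing data become non-response. A withdrawn patient whose score was obtained need not have missing data.

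No link in this chain turns escalation into non-response, so the answer is yes.

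**Step 3. What does the literal Section 7 condition cost?** A remitter with a score below 4 who takes permitted mesalazine fits neither of its branches: the pouchoscopy is not planned, yet the patient is not declared out of remission. If no pouchoscopy follows, week-4 remission on the total mPDAI and week-4 endoscopic improvement are missing and count as non-response. Week-4 response uses the clinical subscore, as do response and remission at weeks 8 and 16; these are unaffected. Omeprazole is dispensed for 14 days, so it should have ended before visit 4 (day 26) and would not by itself trigger the condition.

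**Step 4. Size per patient.** 1/10 = 10 percentage points of an arm's rate. On the planning rates the expected failures are 10 × 0.90 = 9 on placebo and 10 × 0.225 = 2.25 on FMT.

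**Step 5. Illustration for escalation.** The documents give no escalation rate, so the share q of failures scored as successes is an assumption. Placebo rate = 0.10 + 0.90q; FMT rate = 0.775 + 0.225q if both arms are affected. Power is computed as in Step 1.

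| q | Placebo | FMT | Power, both arms | Power, placebo only (FMT 77.5%) |
|---|---|---|---|---|
| 0 | 10.0% | 77.5% | 80.2% | 80.2% |
| 5% | 14.5% | 78.6% | 72.6% | 70.4% |
| 10% | 19.0% | 79.75% | 65.2% | 60.3% |
| 20% | 28.0% | 82.0% | 51.0% | 41.3% |

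**Step 6. Illustration for the pouchoscopy condition.** Let f be the assumed share of true remitters lost in each arm. The rates become 0.10(1 − f) and 0.775(1 − f).

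| f | Placebo | FMT | Power |
|---|---|---|---|
| 10% | 9.0% | 69.75% | 68.9% |
| 20% | 8.0% | 62.0% | 57.2% |
| 30% | 7.0% | 54.25% | 45.3% |

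Step 6 applies the planning rates to week-4 remission on the total score. Section 20 argues its placebo rate from 16 weeks of follow-up, so this table shows sensitivity and is not a forecast.

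**The case against.** Antibiotic-free remission is a coherent target in antibiotic-dependent pouchitis and matches the power statement. The plan's own response to a flare is antibiotic: Section 7 restarts the earlier antibiotic, Section 8 calls for a 10-day course, and no section directs escalation of 5-ASA or steroids. The Section 2 remark concerns topical agents and names neither oral 5-ASA nor systemic steroids. Efficacy is secondary in a 20-patient proof of concept. All of this stands. It makes escalation less likely, but supplies no scoring rule if it occurs.

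A reader might infer that a patient given more steroids is plainly a success. The documents do not support that: Section 8 treats steroid need as lack of efficacy, and a patient withdrawn before week 4 may well have no endpoint data and so be a non-responder. The gap is that this reason is never mapped to the endpoint.

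A reader might also infer that Section 7 fails anyone on any permitted medicine. It does not. The sentence governs planning of a procedure, and the same section defines absence of remission by score or early relapse, never by medication. Taken literally it would catch hormonal contraception and low-dose aspirin too, so loose wording for antibiotics is the likelier explanation. Visit 5 in Section 8 separately says to go ahead with the pouchoscopy in antibiotic-free remitters, so the loss arises only if staff follow Section 7 instead. What remains is a real inconsistency with a limited consequence.

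**Conclusion.** The point holds in two limited parts. As the text stands, a patient controlled by new or increased 5-ASA or steroid treatment after week 0 can be scored as an antibiotic-free remitter or responder at weeks 4, 8 and 16. The condition for the week-4 pouchoscopy also differs between Section 7, Section 8 and footnote a; on the literal Section 7 reading, two week-4 endpoints could be lost for remitters on permitted medicines.

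The only size the documents support is 10 percentage points of an arm's rate per misclassified patient. It would be tempting to say that placebo remission would read 20–30% instead of 10%. That needs one or two of the nine expected placebo failures to be rescued by escalation, and no document gives such a rate. The power figures in Steps 5 and 6 depend in the same way on assumed q and f. The consequence falls on the secondary efficacy estimates intended for the larger trial, not on the primary safety endpoint.

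**What to change.** 1. In Sections 1, 5 and 20, add to each remission and response endpoint that a patient who started or increased 5-ASA, or a topical or systemic steroid, for pouchitis after week 0 is scored as a non-responder. Patients on an unchanged permitted dose stay eligible for success. State that the steroid-related lack-of-efficacy reason in Section 8 maps to non-response. Immunosuppressants, anti-TNF and anti-adhesion drugs need no new wording here, since Section 6 already bars them.
2. Reconcile the condition for the week-4 pouchoscopy across Section 7, Visits 4 and 5 in Section 8, and footnote a in Section 21. Footnote a also uses a different score cut-off (below 4) and adds clinically active patients who decline the open-label extension, so it must be part of the same reconciliation.

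Item 1 changes scoring only, not what patients may receive. It costs endpoint wording and one derived variable from the concomitant-medication record taken at each scoring visit. That record must hold start dates and dose changes, which the documents do not spell out. The downside is that observed remission and response rates may be slightly lower.
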